We expect that exciting the matrix cell-rich areas of the thalamus, such as the ventral anterior section, will lead to a decrease in criterion (c), indicating a shift of the decision criterion towards a more liberal response bias. Conversely, exciting the core cell-rich areas of the thalamus, like the dorsal posterior section, will increase sensitivity (d'), resulting in improved differentiation ability in stimulus perception. Conversely, we also anticipate that inhibiting the ventral anterior thalamus will have the opposite effect on criterion (c), leading to a more conservative decision bias. Inhibiting the dorsal posterior thalamus will reduce sensitivity (d'), resulting in a decreased ability to differentiate between stimuli. By observing these effects, we aim to unravel the distinct causal roles of the anterior and posterior thalamus in conscious perception. This disentanglement will provide valuable insights into the mechanisms of specific thalamic regions in shaping perceptual processes.

Number of Subjects, Recruitment and Informed Consent

Our study will involve the enrollment of 60 participants, who will be randomly assigned to two groups, with each group consisting of 30 participants. The participants will be divided based on the type of transcranial LIFUP they will receive, either excitation or inhibition, targeting four specific thalamic areas. See experimental design details below. Healthy participants will be recruited by listing on UMClinicalStudies.org and by postings at area colleges and community groups in Ann Arbor. Interested volunteers will call the phone number of a designated recruiter for an initial phone screening. The initial phone screening will consist of questionnaires related to medical history, demographic information, handedness, inclusion and exclusion criteria. If interested, the participant will

complete the questionnaires, which will be reviewed by the study team. Once eligibility is confirmed by the study team, the one-time research study session will be scheduled. Participants may be screened for COVID-19 prior to entry into the hospital per hospital guidelines.

[figure not shown]

Figure 3. Randomized study group assignment. A total of 60 participants will be enrolled in the study and randomly assigned to two groups, each comprising 30 participants. The group assignment will be based on the type of transcranial LIFUP they will receive, either in the form of excitation or inhibition.

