LIFUP Method. The mechanism of action of LIFUP have been associated with mechanically induced changes in membrane capacitance, cavitation events, and mechanical sensitivity of voltage-gated ion channels²⁶⁻²⁸. A neuronal intramembrane cavitation excitation model^{29,30}, which accounts for differential effects as a function of cell-type, emerged as an explanation for the stimulus parameter-dependent range of excitatory vs. inhibitory effects. In this model, the LIFUP parameter duty cycle (DC) likely determines excitation (higher DC, allowing for longer sonication-on periods) and inhibition (lower DC, allowing for short ultrasonic bursts with longer periods between bursts) independent of the other sonication parameters. Excitation occurs optimally at a high duty cycle of 70%, allowing for a trade-off in regular-spiking and fast-spiking neurons between charge accumulation during the ultrasound and discharge during the off periods of ultrasound²⁵. In contrast, a low duty cycle (e.g., DC < 10%) produces a suppressive effect³¹⁻³⁹. Thus, LIFUP can bidirectionally modulate the circuitry of interest depending on the choice of duty cycle.

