We will utilize the BrainSonix BXPulsar 1002 LIFUP System (BrainSonix Inc. <http://www.brainsonix.com/>). FDA has determined that our proposed clinical investigation is a nonsignificant risk (NSR) device study because it does not meet the definition of a significant risk (SR) device under 21 CFR 812.3(m) of the investigational device exemptions (IDE) regulation (21 CFR 812). An IDE application is not required to be submitted to, or approved by, FDA for a NSR study. This device contains a single-element, air-backed, spherical section ultrasound transducer with 61 mm diameter and 80 mm focal depth. The transducer is mounted in a plastic housing filled with deionized, de-gassed water and sealed with a thin polyethylene membrane permeable to ultrasound. The transducer will be coupled to the scalp of the participant using a 3D-printed transducer holder that allows for sonication to occur in conjunction with ultrasonic standoff pads and ultrasound gel. The LIFUP system operates at a fundamental frequency of 650 kHz. Following previous work, we plan to administer a pulse repetition frequency of 10 Hz, pulse width of 0.5 ms, and a duty cycle of 70% to induce an excitatory effect and a duty cycle of 5% to induce a suppressive effect. For each thalamic area, a total of 10 sonifications (in 10 minutes) will be administered, with a derated spatial-peak temporal-average intensity (Ispta) of 720 mW/cm², each lasting 30 s, separated by 30 s pause intervals (**Figure 4**). We will utilize the Brainsight Navigation system, developed by Brainbox Ltd, to ensure precise targeting and positioning of the transducer. At the target location, the estimated peak pressure will be 0.71 MPa, and the ultrasound beam width will be 5 mm. The estimated targeting accuracy (uncertainty) at the desired location is ± 2.5 mm. Electromyography (EMG) recordings will complement the behavioral data, providing valuable information about muscle activity and response patterns during the

study.

[figure not shown]

Figure 4. Conceptual illustration of LIFUP setting and parameter configuration (adapted from ³³ and <https://brainsonix.com/technology/>).

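### The stated 10 Hz pulse rate and 0.5 ms pulse width give a 0.5% duty cycle, which is neither the 70% nor the 5% that separates the two randomised arms

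*Combined protocol and SAP*

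**What the plan says.** All references are to the combined protocol and SAP.

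- **Randomised contrast** (Number of Subjects, Recruitment and Informed Consent): "The participants will be divided based on the type of transcranial LIFUP they will receive, either excitation or inhibition", with 30 participants per group.
- **Role of duty cycle** (Methods and Procedures, LIFUP Method): "LIFUP can bidirectionally modulate the circuitry of interest depending on the choice of duty cycle". The same paragraph gives 70% as optimal for excitation and describes values below 10% as suppressive.
- **Settings** (same section): "we plan to administer a pulse repetition frequency of 10 Hz, pulse width of 0.5 ms, and a duty cycle of 70" (per cent, for excitation), and "a duty cycle of 5% to induce a suppressive effect". One frequency and one pulse width are given; only the duty cycle is given by arm.
- **Dose** (same section): 10 sonications per thalamic area, "each lasting 30 s, separated by 30 s pause intervals", at "a derated spatial-peak temporal-average intensity (Ispta) of 720" mW/cm². At the target, "the estimated peak pressure will be 0.71 MPa". Neither value is tied to an arm.
- **Figure 4** is captioned "Conceptual illustration of LIFUP setting and parameter configuration". The figure itself is not reproduced in the copy reviewed.

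**The concern.** Frequency, pulse width and duty cycle are not three free settings: any two fix the third. The plan states all three, and they disagree in both arms.

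This sentence sets the randomised intervention. Someone who programmes the stated frequency and pulse width gives both arms the same 0.5% sonication, which lies in the plan's own suppressive range, and the contrast between arms disappears. Someone who programmes the stated duty cycles must change the frequency, the pulse width or both, and the running text does not say which. Delivery can then be neither reproduced nor checked against that text.

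A second, smaller point follows from the 14-fold ratio of duty cycles. If time-average intensity is the same in both arms, pulse pressure must differ. If pulse pressure is the same, time-average intensity must differ. Anticipated Results and Interpretation predicts opposite effects under excitation and inhibition, so a reader comparing the arms needs to know which quantity changes. This affects interpretation across arms. It does not bias the within-participant comparisons with baseline.

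**Working it through.** **Inputs from the plan:** pulse repetition frequency (PRF) 10 Hz; pulse width 0.5 ms; duty cycle 70% (excitation) and 5% (inhibition); 10 sonications of 30 s per area; Ispta 720 mW/cm²; peak pressure 0.71 MPa.

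**1. Duty cycle from the stated settings.** Duty cycle = PRF × pulse width = 10 × 0.0005 = 0.005 = 0.5%. Ratios: 0.70/0.005 = 140 and 0.05/0.005 = 10. The plan's 70% and 5% are not reproduced.

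**2. Other readings.**
- The 30 s on, 30 s off train taken as the duty cycle: 30/60 = 50%.
- Pulse and train combined: 0.5% × 0.5 = 0.25%.
- A single slip: 5 ms for 0.5 ms, or 100 Hz for 10 Hz, gives 5% but leaves 70% unmet.

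**3. What each arm would need.** These values only show the inconsistency; they are not proposed settings.

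| Duty cycle | Pulse width at 10 Hz | PRF at 0.5 ms | On-time per area (10 × 30 s × duty cycle) |
|---|---|---|---|
| 70% | 70 ms | 1400 Hz | 210 s |
| 5% | 5 ms | 100 Hz | 15 s |
| 0.5% (as stated) | 0.5 ms | 10 Hz | 1.5 s |

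No single PRF and pulse width serves both arms.

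**4. Intensity and pressure, without an impedance assumption.** Ispta = duty cycle × pulse-average intensity (Isppa), and Isppa is proportional to pressure squared. At equal Ispta, the ratio of pressures (5% arm to 70% arm) is √(0.70/0.05) = √14 = 3.7. Any conversion factor common to both arms cancels, so 720 mW/cm² and 0.71 MPa cannot both hold in both.

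**5. Which arm the pair fits.** This step needs assumptions that the documents do not give: a plane wave, acoustic impedance Z of 1.5 to 1.8 MRayl, and a common basis for the derated Ispta and the at-target pressure.
- Isppa = p²/(2Z), with p = 0.71 MPa: 16.8 W/cm² at Z = 1.5 and 14.0 W/cm² at Z = 1.8.
- Implied duty cycle: 0.72/16.8 = 4.3% to 0.72/14.0 = 5.1%.
- Ispta at 0.71 MPa: 70–84 mW/cm² at 0.5%, 700–840 at 5%, and 9,800–11,800 at 70%.
- Pressure at Ispta 720, from p = √(2Z × 0.72/duty cycle) with units converted: 0.66–0.72 MPa at 5% and 0.18–0.19 MPa at 70%.

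Under these assumptions the pair fits the 5% arm approximately. It fits neither the 70% arm nor 0.5%.

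**The case against.** The arithmetic is not in dispute; the objections concern its consequence.

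- **Duty cycle is plainly the controlling parameter.** The LIFUP Method text says that duty cycle likely sets the direction of effect whatever the other settings, and it gives each arm its own value. An operator would have to ignore two explicit instructions to run both arms at 0.5%. This has force: the 140-fold and 10-fold gaps measure a conflict in the text, not an expected dosing error. It still leaves open whether PRF or pulse width changes, and in which arm.
- **Figure 4 may hold settings for each arm.** It may, so the claim is confined to the running text. The caption calls the figure conceptual, and no figure could make the sentence correct.
- **The pressure point rests on unstated physics, and 0.71 MPa is nowhere said to apply to both arms.** The fit to 5% does rest on assumptions. The √14 ratio does not. The missing arm label is itself part of what needs repair.
- **A safety problem should not be inferred.** This stands. The 70% intensities in step 5 are conditional on holding 0.71 MPa. The plan sets Ispta at 720 mW/cm² and, under Procedures for Minimizing Risks, commits to the FDA limit.
- **Any contrast of 70% with 5% must differ in Ispta or in pulse intensity, and no between-arm test is specified.** True. The difference is inherent in the design, and the caveat on interpretation is the least essential part of the remedy.

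**Conclusion.** The concern holds with high confidence and must be fixed. As written, the settings give a 0.5% duty cycle, 140-fold below the excitation value and 10-fold below the inhibition value, and no single frequency and pulse width can produce both stated values. This rests only on the definition of duty cycle. It is an error in the text that sets the randomised intervention, not an omission of detail.

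The secondary point also holds: one Ispta and one pressure cannot both apply to arms whose duty cycles differ 14-fold. Attribution of the pair to the 5% arm depends on the assumptions in step 5. This review does not say which stated value is the right one, and the documents do not show what the device was programmed to deliver. The endpoints, planned analysis and sample size are unaffected.

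**What to change.** Replace the settings sentence with one parameter row per arm:

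- PRF, pulse width and duty cycle, with PRF × pulse width equal to the duty cycle;
- Isppa and peak pressure consistent with an Ispta at or below 720 mW/cm²;
- a statement of which arm the 0.71 MPa estimate describes.

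Make Figure 4 agree with those rows, and confirm that the programmed device settings match them before any participant is sonicated. Optionally, add one sentence to Anticipated Results and Interpretation noting that pulse pressure or Ispta, as well as duty cycle, differs between excitation and inhibition.

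The cost is protocol wording and a check of the device settings, with no extra participants, visits or procedures.

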The novel method of transcranial low-intensity focused ultrasound pulsation (LIFUP) as an attractive alternative that overcomes these limitations. LIFUP has the unique ability to non-invasively target deep brain nuclei, including specific thalamic areas, with remarkable precision of sonication focus²⁴. Despite the growing body of literature on LIFUP-induced behavioral modifications²⁵, its effect on conscious perception remains largely unexplored. Employing LIFUP to noninvasively modulate the activity of select brain regions has the potential to shed light on the intricate neural mechanisms of conscious perception in humans.

Research Objectives

The primary objective of this study is to investigate the causal role of thalamic areas in conscious perception using LIFUP. We hypothesize that stimulating different thalamic regions by LIFUP will result in distinct perceptual outcomes, potentially affecting subjective perception as quantified by criterion and detection sensitivity as described in detail under Data Analysis and Statistics.

To test these hypotheses, we have devised a three-fold approach:

1. We will conduct a near-threshold perceptual task to assess the perceptual outcomes under different conditions.

2. Utilizing transcranial LIFUP, we will selectively stimulate (both excite and inhibit) the anterior and posterior thalamic areas. These areas are chosen because they are known to be differentially enriched by matrix and core thalamic cells, respectively.
3. We will evaluate the quality of conscious contents using two orthogonal quantities derived from Signal Detection Theory: criterion (c) and sensitivity (d'). Criterion (c) represents a subject's tendency to report subjective recognition of a target stimulus, irrespective of its presence or absence. On the other hand, sensitivity (d') measures a subject's ability to differentiate between trials with a target present and trials with a target absent (**Figure 2**).

— Hit — Correct Rejection
— Miss — False Alarm

[figure not shown]

Figure 2. An overview of Signal Detection Theory

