Experimental Design. The experimental will consist of a 10-minute baseline period (LIFUP-OFF) followed by four 10-minute sessions of stimulating (LIFUP-ON) four thalamic areas. The order of thalamic area stimulation will be counterbalanced across participants and will include the ventral anterior (VA), dorsal anterior (DA), ventral posterior (VP), and dorsal posterior (DP) sections of the thalamus. The center coordinates of these thalamic regions will be derived from a previous study on thalamic parcellation ⁴⁰. Given that previous studies have not indicated any functional lateralization of the thalamic areas, we will target only the left hemisphere for the sake of convenience in this study.

Perceptual Task. The quality of conscious perception will be assessed by a well-established psychometric approach, the near-threshold perceptual task ^{41,42}. This task allows one to compare the neural activity evoked by identical weak stimuli that are sometimes perceived and sometimes remain subliminal (**Figure 5**). It thus rules out potential confounds of variability derived from the differences in physical property of the stimuli. All stimuli will be programmed using E-Prime (Psychology Software Tools, Pittsburgh, PA) and delivered via a laptop computer. Stimuli will be presented at the threshold of subjective recognition. An adaptive thresholding procedure will be conducted whereby image contrast will be titrated to reach a 50% subjective recognition rate for each subject. Stimuli will include two common visual object categories: faces and houses. Participants' task is to report the category ("F" or "H") of an image presented and their recognition experience ("Yes" or "No"). Specifically, they will be instructed to report the object category regardless of their recognition experience and, in cases of unrecognized images, to make a genuine guess (two-alternative choice discrimination). Then, they will be instructed to report whether they see an object, such that even if the object appears unclear or noisy, they should respond "yes", but if they see nothing or only low-level features, they should respond "no".

[figure not shown]

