Figure 5. Visual task design. During each 10-min session, participants will complete an image recognition task. Stimuli (faces, houses, and scrambled images) will be presented at the threshold of subjective recognition. Participants' task is to report the category ("F" or "H") of the image presented and their recognition experience ("Yes" or "No").

The stimulus set will include real and scrambled images, the latter will be created by phase-shuffling of a randomly chosen real image from each category to preserve category specific low-level image features^{41,42}. Because scrambled images serve as "catch trials" to determine the subjects' baseline tendency to give positive responses to a question about their recognition experience. The pre-stimulus interval will vary randomly from trial to trial between 2 and 4 seconds to prevent stimulus timing predictability. The stimuli will be presented in a randomized order to prevent category predictability.

Primary Outcome Measure

Perceptual criterion (c) and sensitivity (d') derived from the Signal Detection Theory (SDT) analysis. These measures will be assessed over a timeframe spanning from the baseline to 60 minutes after the LIFUP stimulation.

Data Analysis and Statistics

For each 10-min session, we will calculate sensitivity (d') and criterion (c) using subjective reports of recognition as "yes" or "no". (d') indicates the ability to discriminate between real and scrambled images. It is computed by subtracting the z-transformed False Alarms Rate (FAR) from the z-transformed Hit Rate (HR): $d' = Z(HR) - Z(FAR)$, where Z is an inverse normal cumulative distribution function. (c) reflects the tendency to make "yes" reports to indicate recognition, regardless of whether the stimulus is a real or a scrambled image, which is computed as: $c = -0.5 \times (Z(HR) + Z(FAR))$. We will also calculate percent of correct responses as an operational measure of two alternative-forced-choice sensitivity using subjective category reports, i.e., responses to the first question: "Face" or "House".

We will conduct a repeated-measures ANOVA, considering measurements taken during both the baseline and the four thalamic areas' stimulation sessions. This analysis will be

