performed at the group level to assess the effects of LIFUP on the perceptual measures. To determine statistical significance, we will apply a false discovery rate (FDR) correction and set the threshold at $\alpha < 0.05$. This approach will help us identify any significant differences between the baseline and the different thalamic area stimulations in terms of sensitivity (d') and criterion (c).

Anticipated Results and Interpretation

We expect to observe differential changes in the perceptual outcomes based on the LIFUP stimulation of different thalamic areas. We anticipate that stimulation of the ventral anterior thalamus will decrease criterion (c), indicating a shift of the decision criterion in the liberal direction. During exciting the dorsal posterior thalamus, we expect an increase in sensitivity (d'), reflecting a higher sensitivity in differentiating between stimuli. Conversely, when inhibiting the ventral anterior thalamus and the dorsal posterior thalamus, we expect the opposite effects on criterion (c) and sensitivity (d') compared to the outcomes seen during their respective excitations. The effects of stimulating the dorsal anterior thalamus and the ventral posterior thalamus are expected to lie between the effects of ventral anterior and dorsal posterior thalamic stimulation. These findings should provide valuable insights into the specific contributions of these thalamic regions in shaping conscious experiences.

Power Analysis

We considered a recent review article that summarized 25 LIFUP studies in humans. These studies had sample sizes ranging from 1 to 50, with a median value of 16. Since the neuromodulation effect is dependent on various factors, such as parameter settings and specific brain regions targeted, determining a prior effect size is challenging. However, we have planned a subject number of 30 per group, which exceeds the median sample size reported in the literature. With a larger sample size, we aim to enhance the statistical power, reliability and sensitivity of our findings, enabling us to draw robust conclusions about the neuromodulatory effects of LIFUP on conscious perception.

Biological Variables

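### The no-stimulation block always comes first, so the baseline-versus-area comparisons cannot separate stimulation from any change after block 1, and the comparisons that could are not named as tests

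*Combined protocol and SAP*

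**What the plan says.** **Design.** Methods and Procedures, Experimental Design: "The experimental will consist of a 10-minute baseline period (LIFUP-OFF) followed by four 10-minute sessions of stimulating (LIFUP-ON) four thalamic areas". On order: "The order of thalamic area stimulation will be counterbalanced across participants". The OFF period is not part of that counterbalancing and never occurs in blocks 2 to 5.

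**Arms.** Under Number of Subjects, Recruitment and Informed Consent there are 60 participants "who will be randomly assigned to two groups, with each group consisting of 30 participants". They are "divided based on the type of transcranial LIFUP they will receive, either excitation or inhibition, targeting four specific thalamic areas". No sham arm and no later OFF block is described.

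**Analysis.** Data Analysis and Statistics states: "We will conduct a repeated-measures ANOVA, considering measurements taken during both the baseline and the four thalamic" areas' sessions. It is run at group level with an FDR correction at 0.05, and its stated use is to "identify any significant differences between the baseline and the different thalamic area stimulations" for d' and c. It does not name an arm factor, an arm-by-session interaction, an area-versus-area contrast or a position term.

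**Aim.** Research Objectives: "The primary objective of this study is to investigate the causal role of thalamic areas in conscious perception using LIFUP". The protocol also expects ventral anterior (VA) stimulation to move c, dorsal posterior (DP) stimulation to move d', and the signs to reverse between the arms. These are stated as expectations, not as tests.

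**The concern.** Every participant does the task unstimulated once, in block 1, and stimulated in blocks 2 to 5. Within an arm, any change after block 1 has the same signature as a LIFUP effect common to the areas. Image contrast is titrated for each subject, but no re-titration between blocks is described, so nothing written holds performance constant over five blocks. The documents do not say whether c or d' drifts, or by how much.

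A causal claim is at stake on both primary outcomes. A baseline-versus-area difference in one arm could be reported as an effect of stimulating that area when it reflects time on task. FDR control limits chance findings among several tests; it does nothing about a bias that all of them share.

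**Working it through.** **1. The plan's own figure.** There is none on this point to reproduce. The 30 per group rests on exceeding a literature median of 16, with no effect size, SD or power given. Only 2 × 30 = 60 and 30 > 16 can be checked, and both hold.

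**2. Identification, with no drift assumption.** Take the 24 possible area orders, one subject each, five sessions, and a model with subject, session position and condition effects.
- Free parameters needed: 24 subjects + (5 − 1) positions + (5 − 1) conditions = 32.
- Rank of the design: 31, because the indicator for OFF equals the indicator for position 1.
- VA minus OFF is not estimable within an arm, and remains so when both arms share position effects in one model.
- VA minus DP is estimable. So is the between-arm difference in (VA minus OFF), with position effects common to the arms.

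**3. Size for one comparison.** Inputs: n = 30 per arm and 5% from the protocol; two-sided testing and drift δ (in SDs of the paired ON−OFF difference) are assumed. With no stimulation effect, a paired t-test has 29 df and noncentrality δ√30:
- δ = 0.2: 1.10, rejects 18.5%
- δ = 0.3: 1.64, rejects 35.5%
- δ = 0.5: 2.74, rejects 75.4%

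**4. Size for the planned analysis.** Simulation with 10,000 trials per cell and no LIFUP effect. Assumed: independent session noise, Benjamini–Hochberg over the four areas, and areas allocated over the 24 orders (24 plus 6 at random per arm). The step drift is at full size in blocks 2–5. The linear drift is at 1/4, 2/4, 3/4 and 4/4 of full size.

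| Rejection, at drift 0.2 / 0.3 / 0.5 SD | Step | Linear |
|---|---|---|
| At least one FDR-significant area in an arm | 22 / 43 / 87% | 11 / 19 / 46% |
| Five-session ANOVA | 16 / 33 / 79% | 9 / 15 / 34% |
| VA significant with one arm's predicted sign (drift in the favourable direction) | 11 / 26 / 69% | 5 / 9 / 26% |
| Between-arm comparison of change; VA vs DP | 4–6% | 4–6% |

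At zero drift the first row is 5%. Both arms significant in opposite directions occurred in 0 of 10,000 trials.

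The two shapes differ mainly in average drift. The linear form averages (1/4 + 2/4 + 3/4 + 1)/4 = 0.625 of its final size, so 0.5 SD at block 5 averages 0.31 SD, and its 46% is close to the 43% for a 0.3 SD step.

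**5. Power of the alternatives.** Two-sided 5%, one comparison, unadjusted. The within-arm test has noncentrality d√30. The between-arm test has noncentrality D√(30/2), where D = 2d if the arms move equally and oppositely and D = d if only one responds.

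| Effect d | Within-arm baseline test | Between arms, opposite | Between arms, one responds |
|---|---|---|---|
| 0.5 SD | 75% (2.74) | 97% (3.87) | 48% (1.94) |
| 0.3 SD | 36% (1.64) | 63% (2.32) | 21% (1.16) |

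At the strictest step of a four-test Benjamini–Hochberg procedure (0.0125), the 0.5 SD row becomes 54%, 90% and 27%.

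**6. Carry-over into area contrasts.** Suppose a fraction q of an effect persists per session. Over the 24 orders, VA precedes DP by one, two or three sessions with probability 1/4, 1/6 and 1/12. The mean share of the VA effect present in the DP session is then q/4 + q²/6 + q³/12: 7%, 18%, 32% and 50% at q = 0.25, 0.5, 0.75 and 1.

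**The case against.** The strongest defence is that the hypothesis is a pattern, not simply ON versus OFF: VA moves c, DP moves d', and the signs reverse between arms. A drift common to areas and arms cannot produce that. This is right, and it limits the damage to single-arm, single-area claims. But no planned test uses the pattern, and nothing in the plan stops one arm's baseline difference from being reported alone.

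The analysis text can also be read generously. The five-session ANOVA contains area-to-area variation, and analysis at group level might be meant to include arm as a factor. The wording is indeed ambiguous. However, the ANOVA includes the baseline and so shares the contamination, and no interaction is written.

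Titration to threshold implies some task exposure before block 1, which may reduce early practice effects. It does not remove later fatigue or adaptation. Gradual drift could also be checked in blocks 2–5: under the linear drift above, a slope test pooling all 60 participants would detect 0.2, 0.3 or 0.5 SD with probability 22%, 44% or 85%. With a strictly linear position effect, VA minus OFF becomes estimable by extrapolation. The plan neither schedules such a check nor makes that restriction, and the check cannot see a step between blocks 1 and 2.

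Finally, the largest rates combine the least favourable shape with the largest size shown. That is so, which is why the range is given.

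**Conclusion.** The concern holds. The aliasing follows from the design text and needs no assumption about drift. Within an arm, the named baseline-versus-area differences cannot be attributed to stimulation unless a drift shape is imposed. The five-session ANOVA is contaminated rather than wholly aliased.

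How often this would mislead depends on drift of unknown size and shape: from 11% (linear, 0.2 SD) to 87% (step, 0.5 SD) for at least one false FDR-significant area in an arm, against 5% without drift. These rates assume independent session noise and an FDR family of four areas. The comparison between randomised arms and the counterbalanced area contrasts keep close to their nominal error under drift common to both arms, and the trial as designed can already supply them. Area contrasts remain open to carry-over, since no interval between sessions is described.

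**What to change.** Before any data are analysed, amend Data Analysis and Statistics to:
- name as confirmatory (a) the arm-by-session interaction, that is, ON-minus-OFF change compared between the excitation and inhibition arms, and (b) the counterbalanced area contrasts such as VA versus DP;
- include session position (2 to 5) in the model, with preceding area as a sensitivity term;
- label within-arm baseline-versus-area tests descriptive.

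Also state whether the physical set-up in the OFF block matches the ON blocks. Separately, reconcile the Primary Outcome Measure text ("These measures will be assessed over a timeframe spanning from the baseline to 60 minutes after the LIFUP stimulation") with the five sessions analysed; the conclusion here does not depend on it.

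**Cost.** Analysis wording and one sentence on set-up, with no extra visit time. There are three real losses:
- Claim (a) becomes that excitation differs from inhibition, not that either differs from no stimulation. The latter would need a sham or an OFF block placed among the ON blocks.
- Power for (a) rises if the arms move oppositely, as the protocol predicts, but at 0.5 SD falls from 75% to 48% if only one arm responds. VA versus DP keeps 75% at 0.5 SD if only one of the two areas moves that measure, assuming independent session noise.
- Any sensation that differs between the two stimulation modes would remain in (a).
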